## **Objectives:**

To investigate the effect of RECO-18 pretreatment on pregnancy outcomes of IVF/ICSI in infertile women when compared with oral administration of multi-vitamins.

## **Design:**

This study is a prospective, randomized, controlled and superiority clinical trial.

## **Participants:**

Eighty infertile patients undergoing IVF/ICSI are randomized to either RECO-18 treatment or multi-vitamins with the ratio of 1:1.

## **Inclusion criteria**

- female, 20 to 40 years old;
- the 1st or 2nd cycle of IVF/ICSI treatment;
- BMI  $\leq$  30Kg/m^2, 4) with bilateral ovaries;
- be eligible for IVF/ICSI treatment.

## **Exclusion criteria**

- repeated implantation failures (with previous 3 or more IVF/ICSI failures);
- moderate to severe endometriosis;
- untreated hydrosalpinx;
- untreated endometrial disease;
- contraindications for assisted reproductive techniques or gestation;
- a history of ovarian surgery;
- expected poor ovarian response (POR) or previous POR;
- polycystic ovarian syndrome;
- participants in clinical trials of other drugs within one month prior to enrollment;
- hypersensitivity to follicle-stimulating hormone- $\alpha$ , FSH, human menopausal gonadotropin, LH or excipients;
- uncontrolled endocrine diseases (such as hyperthyroidism, hypothyroidism, adrenal gland disease, obesity, etc.);

- percutaneous epididymal sperm aspiration or testicular sperm aspiration.

**Research procedure:**

Eighty infertile patients undergoing IVF/ICSI are randomized to either RECO-18 treatment (treatment group, n=40) or multi-vitamins (control group, n=40).

The treatment group begins to take Reco-18 on the 1st to 5th day of menstruation with a dosage of 4 pills per day for the whole menstrual cycle, then perform ovulation induction on the second menstrual cycle, and continue to take Reco-18 until the day of oocyte retrieval.

The control group takes the multi-vitamins (Elevit, Bayer S.A.) with the dosage of one tablet per day as the same period in the treatment group.

**Primary and secondary outcomes**

The primary outcome is the ongoing pregnancy rate at 12 weeks' gestation;

The secondary indicators are the number of oocytes retrieved, normal fertilization rate, the high quality embryos rate, implantation rate, clinical pregnancy rate, and early miscarriage rate.

**Statistical analysis:**

Data are analyzed using SPSS 19.0 statistical software. Measurement data are expressed as mean ± standard deviation, and categorical variables are described as percentages. Data are compared using the independent sample t-test or chi-squared test. P<0.05 is considered statistical significance.

**Plan of follow-ups:**

	Screening and randomization	IVF/ICSI treatment		Follow-up		
	V1	V2	V3	V4	V5	V6
	Before IVF/ICSI treatment	IVF/ICSI treatment cycle	Thawed ET cycle	2 weeks after ET	4-5 weeks after ET	12 weeks of gestation
Informed consent	√					
Eligibility Criteria	√					
Personal information	√					
History	√					
Companied medication	√	√	√	√	√	√
Physical examination	√					
Vital signs	√	√	√			
Sex hormones	√	√	√			
Ultrasound	√	√	√		√	√
Complication and adverse events		√	√	√	√	√

## **1. Study protocol summary**

How to improve the fertility of infertile women has become a hot topic in the field of reproductive medicine. Animal experiment has shown that RECO-18 significantly improved the female fertility in mice, and the specific mechanism was related to reducing follicular atresia, promoting follicle development and improving oocyte quality. Therefore we aim to conduct a pilot study to explore the effect of RECO-18 in infertile women undergoing in vitro fertilization-embryo transfer (IVF-ET). This study is a prospective, randomized, controlled clinical study. The treatment group takes RECO-18 while the control group takes the multi-vitamins. The primary indicator is the ongoing pregnancy rate at 12 weeks' gestation; the secondary indicators are the number of oocytes retrieved, normal fertilization rate, the high quality embryos rate, implantation rate, clinical pregnancy rate, and early miscarriage rate.

## **2. Research background**

In recent years, the group of infertile women has gradually expanded with the effect of environmental pollution, diet and sleeping habits. The decline of female fertility is manifested with decreased ovarian reserve and poor oocyte quality. With the increasing education and social status improvement in female, more and more women have postponed their childbearing plans. It is reported that the average childbearing age of women is nearly 30 years old in our country. Moreover, the liberalization of two-child and three-child policy maybe further delays female reproductive age. Therefore, how to improve the female fertility has become a social and scientific problem in China, and it is urgent to develop new technologies and products to improve the fertility of infertile women.

In female mammals, a follicle is the basic functional unit of the ovary, consisting of an oocyte and single or multiple layers of granule cells. According to the different stages of the oocytes, there are primordial follicle, primary follicle, secondary follicle, antral follicle, and preovulatory follicle. Primordial follicles locate in the resting follicle pool of the ovary with a certain number. The number of human primordial follicles in the ovaries at birth is around 400,000, and decreases with age. When the number of primordial follicles decreases to less than 1000, a female enters the menopause at about 51 years old with disabled fecundity [1, 2]. The optimal age for childbearing is around 25 years old, and ovarian function begins to decline in 30 years old. After the age of 35, ovarian reserve decreases dramatically with the acceleration of primordial follicle activation, meanwhile oocyte quality is declining with the manifestation of high proportion of mature oocyte aneuploidy, low fertilization rate and embryo implantation rate, and high miscarriage rate. Ageing woman is suggested to consult in assisted reproductive center if she has prepared for pregnancy over 6 months but fails in conception. However, it is noteworthy that the success probability of assisted reproduction technology (ART) in aging woman is relative low, because traditional ovarian stimulation is not very effective. Oocyte donation is the effective treatment for aging woman with low fecundity or even infertility, but most women want to have their own babies, and hardly accept it in the mind. Personalized ovarian stimulation protocol and preimplantation

genetic testing are used as clinical intervention, but the treatments increase the costs, and low chance of pregnancy still exists. It is closely related to poor oocyte quality caused by ovarian aging. Therefore, how to protect ovarian reserve and improve oocyte quality is the key to improve female fertility [3-5].

Granulosa cells differentiate into mural granulosa cells and cumulus cells at the stage of the secondary follicle. The cumulus cells are connected to the oocyte by gap junctions, and gradually separate from the mural granulosa cells to form follicular cavity. The follicular cavity is filled with follicular fluid composed of plasma exudate and local secretions, which constitutes the internal environment of oocyte development and plays an important regulatory role in follicular development, maturation, ovulation and atresia. In the process of ovarian aging, the ovarian chronic inflammatory environment and angiogenesis abnormality around the follicle increase the oxidative stress level, decrease mitochondrial vitality, and increase cell apoptosis level, which lead to abnormal granulosa cell function and follicular microenvironment changes, and finally oocyte is damaged with poor quality. Human preovulatory follicular fluid contains a large number of antioxidant enzymes, such as CAT, GSSPx, GST, etc, which mainly prevent the damage of oxidative stress to oocytes. The decreased level of GST and CAT and increased SOD activity are observed in the follicular fluid of aging woman. The decrease in the CAT / SOD ratio indicates a diminished scavenging ability of activating oxide in the follicle [6, 7]. Due to the important role of oxidative stress in ovarian aging, a large number of studies have shown that the application of antioxidants such as Vitamin C, Vitamin E and CoQ 10 effectively improve oxidative stress levels in oocytes, restore mitochondrial function and improve oocyte quality [8-10]. In 2021, consensus on reproductive health and multiple micronutrient in China recommends that infertile woman takes multiple micronutrient containing folic acid of 0.8mg before ART or on the day of embryo transfer to reduce the risk of neural tube defects. However, the adjuvant drugs have not been fully confirmed in evidence-based medicine clinical research, and have not been routinely recommended to aging woman in the guideline.

Mitochondrial function is closely related to oocyte quality, and the effects may be more pronounced in infertile woman. The lack of multiple micronutrients is more common in infertile woman, and the supplementation of multiple micronutrients has an antioxidant effect, which reduce the damage of oxidative stress to fertility and help to improve the outcomes of ART. RECO-18 is a functional food containing a variety of plant extracts (sophora flower bud, clove, yam) and enzymatic soybean phospholipids, and its specific nutrients are list in Table 1. In previous in vivo and in vitro senescent models, RECO-18 was found to improve oocyte quality mainly by regulating the mitochondrial apoptosis pathway. Animal experiment has shown that RECO-18 significantly improved the female fertility in mice (Figure 1, Figure2, Figure 3), and the specific mechanism was related to reducing follicular atresia, promoting follicle development and improving oocyte quality. Therefore we aim to conduct a pilot study to explore whether RECO-18

plays a role in improving oocyte and embryo quality and pregnancy outcomes in infertile women undergoing IVF-ET.

Table 1. Nutrients of RECO-18

Project	Per 100g
Energy	1860kJ
Protein	20.2g
Fat	14.9g
Carbohydrate	56.8g
Sodium	334mg
Vitamin A	14072 $\mu$ gRE
Vitamin D	245.0 $\mu$ g
Vitamin B 1	57.00mg
Vitamin B 2	35.70mg
Vitamin B 6	47.00mg
Vitamin B 12	64.20 $\mu$ g
Vitamin C	2801.0mg
Niacin	347.00mg
Folic acid	9527 $\mu$ g
Iron	447.0mg
Zinc	202.00mg

[figure not shown]

Figure 1: RECO-18 improved oocytes quality in in vitro and in vivo senescent models. A and C, RECO-18 improved mitochondrial distribution in in vitro aging COC; B and D, RECO-18 reduced ROS level in in vitro aging COC; E and G, RECO-18 reduced TUNEL fluorescence signal in in vivo aging COC ; F and H, RECO-18 reduced ROS level of oocytes in in vivo aging COC.

[figure not shown]

Figure 2: RECO-18 improved the aging oocyte quality mainly by improve the mitochondrial apoptosis pathway of cumulus cells. A and B, Western blot showed that RECO-18 improved the apoptosis pathway in aging COC; C, RECO-18 improved the mitochondrial distribution in aging COC; and D and E, RECO-18 increased the cardiolipin level in aging COC; F and G, RECO-18 reduced cytochrome C level in aging COC.

[figure not shown]

Figure 3: RECO-18 improved oocyte quality and fertility in aging mice. A, RECO-18 increased pregnancy rate of aging mice; B, RECO-18 increased litter size of aging mice; C, RECO-18 increased the weaning weight of offspring in mice; D, RECO18 increased the ovulation of aging mice; E, RECO-18 reduced the fragmentation rate of oocyte in aging mice during ovarian stimulation; F and G, RECO-18 improved the mitochondrial membrane potential of oocyte in aging mice.

### 3. Research purpose

To investigate the effect of RECO-18 pretreatment on pregnancy outcomes of IVF-ET in infertile women when compared with oral administration of multi-vitamins.

### 4. Research design

This study is a prospective, randomized, controlled and superiority clinical trial. Subjects will be recruited from the infertile patients undergoing IVF/ICSI at the Reproductive Medicine Center of Sun Yat-sen Memorial Hospital, Sun Yat-sen University.

The treatment group begins to take Reco-18 on the 1st to 5th day of menstruation with a dosage of 4 pills per day for the whole menstrual cycle, then perform ovulation induction on the second menstrual cycle, and continue to take Reco-18 until the day of oocyte retrieval. The control group

takes the multi-vitamins (Elevit, Bayer S.A.) with the dosage of one tablet per day as the same period in the treatment group.

## **5. Research protocol**

### 5.1 Sample size

At first it is designed to include 80 infertile patients (40 cases in each group), then the sample size is calculated based on the preliminary study results.

### 5.2 Inclusion criteria

- female, 20 to 40 years old;
- the 1st or 2nd cycle of IVF/ICSI treatment;
- BMI  $\leq$  30Kg/m^2, 4) with bilateral ovaries;
- be eligible for IVF/ICSI treatment.

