### 5.3 Exclusion criteria

- repeated implantation failures (with previous 3 or more IVF/ICSI failures);
- moderate to severe endometriosis;
- untreated hydrosalpinx;
- untreated endometrial disease;
- contraindications for assisted reproductive techniques or gestation;
- a history of ovarian surgery;
- expected poor ovarian response (POR) or previous POR;
- polycystic ovarian syndrome;
- participants in clinical trials of other drugs within one month prior to enrollment;
- hypersensitivity to follicle-stimulating hormone- $\alpha$ , FSH, human menopausal gonadotropin, LH or excipients;
- uncontrolled endocrine diseases (such as hyperthyroidism, hypothyroidism, adrenal gland disease, obesity, etc.);
- percutaneous epididymal sperm aspiration or testicular sperm aspiration.

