### 5.4 Exit criteria

1) Patients request to drop out; 2) the cycle is cancelled due to low ovarian response or premature ovulation; 3) actual treatment deviates from the protocol; 4) patients lost follow-up.

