### 5.5 The measurement of research results

Primary indicator: the ongoing pregnancy rate at 12 weeks' gestation.

Secondary indicators: the number of oocytes retrieved, the normal fertilization rate and the rate of high quality embryos, implantation rate, clinical pregnancy rate, and early miscarriage rate.

Randomization: randomized envelope method is used in the study. Random sequence is firstly generated by an independent statistician, secondly the grouping is randomized according to

random number and put into an opaque sealed envelope by the independent personnel, at last the investigator divides the subjects in line with the sealed envelope.

Random ratio: 1:1

Grouping: the treatment group takes RECO-18 while the control group takes the multi-vitamins.

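### RECO-18's evidence comes from ageing models, yet randomisation to a 20-40 sample has no age stratum and the primary rate test is unadjusted for age

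*Combined protocol and SAP*

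**What the plan says.** **Population.** Section 5.2 admits participants who are "female, 20 to 40 years old". Section 5.3 removes women with "expected poor ovarian response (POR) or previous POR". The objective (synopsis and section 3) is the effect on IVF pregnancy outcomes in infertile women, with no age qualifier.

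**Evidence for the product.** Section 2 reports: "In previous in vivo and in vitro senescent models, RECO-18 was found to improve oocyte quality". Figures 1 and 2 concern ageing oocyte complexes. The Figure 3 caption reads: "RECO-18 improved oocyte quality and fertility in aging mice". Sections 1 and 8.2 summarise the mouse data without saying that the animals were ageing.

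**Age in the background.** Section 2 places the start of ovarian decline at 30 and adds: "After the age of 35, ovarian reserve decreases dramatically with the acceleration of primordial follicle activation". Of the low chance of pregnancy in ageing women it says: "It is closely related to poor oocyte quality caused by ovarian aging".

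**Randomisation.** Section 5.5 uses sealed envelopes, 1:1: "Random sequence is firstly generated by an independent statistician". No stratification factor or block is named.

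**Analysis.** Section 7.2 compares ongoing pregnancy at 12 weeks by a two-sample rate test (Pearson chi-squared or Fisher). A logistic model then examines baseline effects, with age first in its list of factors. No age subgroup and no treatment-by-age term is planned.

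**The concern.** The step from ageing oocytes to women aged 20-40 is not argued anywhere in the protocol. That leaves two practical matters.

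The first is interpretation. Animal and laboratory data from ageing models are indirect evidence for a sample that may be mostly under 35 and that leaves out expected and previous poor responders.

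The second is the comparison itself. The protocol treats age as related to oocyte quality and pregnancy, but with 40 women per arm nothing in the allocation keeps age balanced. The test named first for the primary outcome makes no correction. If the crude and age-adjusted results differ, the plan does not say which one carries the conclusion.

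**Working it through.** The documents give no age mix, no pregnancy rates and no derivation of the 80 patients, so there is no planned figure to reproduce. What can be checked is how far chance imbalance in age could move an unadjusted comparison.

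**Inputs**

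- From the documents: n = 40 per arm, 1:1 (sections 5.1 and 5.5); age 35 as the point of marked decline (section 2).
- Assumed: share f of women aged 35 or over = 25%, with 15% and 40% as a range; ongoing pregnancy rate 50% under 35 and 30% at 35 or over, a gap of 20 points.

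**1. Size of chance imbalance.** The SD of the between-arm difference in the share aged 35 or over is √(2 × f × (1 − f) / 40).

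| f | SD | 1.96 × SD |
|---|---|---|
| 15% | √(2 × 0.15 × 0.85 / 40) = 0.080 | 0.16 |
| 25% | √(2 × 0.25 × 0.75 / 40) = 0.097 | 0.19 |
| 40% | √(2 × 0.40 × 0.60 / 40) = 0.110 | 0.21 |

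By the hypergeometric distribution (80 women, 40 per arm), the chance that the arms differ by 10 points or more is 40%, 47%, 49% and 50% at older shares of 20%, 30%, 40% and 50%.

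**2. Effect on the crude difference.** The shift is the imbalance times the gap in rates.

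- 10-point imbalance: 0.10 × 20 = 2 points.
- 19-point imbalance (the 95% limit at f = 25%): 0.19 × 20 = 3.8, about 4 points.

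**3. Comparison with sampling error.** At rates near 50%, the 95% half-width of the crude difference is 1.96 × √(2 × 0.5 × 0.5 / 40) = 0.219, about 22 points. Age imbalance is therefore a small part of the total uncertainty. At f = 25% the mean rate is 0.25 × 30 + 0.75 × 50 = 45%. The part of the outcome variance due to the age split is 0.25 × 0.75 × 0.20² = 0.0075, out of 0.45 × 0.55 = 0.2475, or about 3%.

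**4. What an estimate within the older stratum could show.** At f = 25% there are 40 × 0.25 = 10 older women per arm. With assumed rates of 30% and 50%, the 95% half-width is 1.96 × √(0.3 × 0.7/10 + 0.5 × 0.5/10) = 1.96 × 0.214 = 0.42, or about 42 points. With a 20-point benefit in older women only, power for a treatment-by-age interaction is about 12-15% at older shares of 20-50%. Results by age can only be descriptive.

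**The case against.** The strongest reply is that the sample matches the stated objective. Sections 1 to 3 name infertile women undergoing IVF, and section 2 also offers a rationale not tied to age: micronutrient deficiency in infertile women and the oxidative damage it allows. A first pilot often rests on indirect laboratory evidence. Age is recorded at baseline (5.8.1) and is already an adjustment factor, together with AMH and AFC.

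Most of this stands. It limits the point to indirectness and imbalance, but it does not remove it. The control arm also takes multi-vitamins, so micronutrient supply is offered to both arms (though composition may differ), and the evidence shown for RECO-18 itself still comes from ageing models. The logistic model adjusts for age but is separate from the rate test named for the primary outcome.

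A reader might go further and infer that the trial averages away the very group its hypothesis concerns, so that a null result would not test the mechanism. If a 20-point benefit existed only at 35 or over, the overall difference would be 20 × 0.15 = 3, 20 × 0.25 = 5 or 20 × 0.40 = 8 points at shares of 15%, 25% or 40%. The documents do not support that reading:

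- The hypothesis is not stated for older women, and no claim is made for them.
- The calculation needs zero benefit below 35, whereas section 2 has decline beginning at 30.
- Women of 35 to 40 are eligible, and excluding poor responders removes low-response women, not older women as such.
- Low power is a problem of sample size: 40 per arm gives about 43-45% power even for an undiluted 20-point difference (control rates 30-50%, two-sided 5%).

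**Conclusion.** The point holds as a modest and cheap improvement. The RECO-18 evidence is indirect for a 20-40 population, and the plan leaves an age-related outcome open to chance imbalance in an unadjusted primary test. At an assumed 25% older share and a 20-point gap in rates, the likely disturbance is about 2 to 4 points, well inside the sampling error of about 22 points. A different age mix or gap would change these figures.

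It would be wrong to conclude that the eligibility range is an error, that the plan contradicts itself, or that the protocol calls age decisive. Section 2 gives that weight to ovarian reserve and oocyte quality.

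**What to change.** Leave eligibility as it is.

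- **Section 5.5:** have the independent statistician generate the envelope sequence in two age strata (under 35; 35 or over), using permuted blocks of varying size that are concealed from the investigator who opens the envelopes.
- **Section 7.2:** account for the stratum in the primary comparison, for example by a stratum-adjusted risk difference with a 95% confidence interval, and name that as the primary result.
- **Optional:** add one descriptive table of ongoing pregnancy by age stratum, labelled exploratory and too imprecise for inference.
- **Interpretation:** state why ageing-model evidence is taken to apply at 20-40, and word the overall conclusion for women aged 20-40 with expected normal response.
- **Section 5.1:** do not base the definitive trial's sample size on the stratum estimates.

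The cost is a second set of envelopes and slightly more analysis work. Incomplete blocks may leave the arms a little off 40:40. If allocation has already begun, the analysis change can still be fixed before database lock.

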### 5.3 Exclusion criteria

- repeated implantation failures (with previous 3 or more IVF/ICSI failures);
- moderate to severe endometriosis;
- untreated hydrosalpinx;
- untreated endometrial disease;
- contraindications for assisted reproductive techniques or gestation;
- a history of ovarian surgery;
- expected poor ovarian response (POR) or previous POR;
- polycystic ovarian syndrome;
- participants in clinical trials of other drugs within one month prior to enrollment;
- hypersensitivity to follicle-stimulating hormone- $\alpha$ , FSH, human menopausal gonadotropin, LH or excipients;
- uncontrolled endocrine diseases (such as hyperthyroidism, hypothyroidism, adrenal gland disease, obesity, etc.);
- percutaneous epididymal sperm aspiration or testicular sperm aspiration.

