#### 6.2 Adverse events report:

Mild adverse events are recorded in the progress note.

Serious adverse events are submitted to Medicine Ethics Committee within 48 hours of occurrence.

6.3 Safety indexes are adverse events occurring in the treatment group and the control group, such as gastrointestinal reactions and allergies.

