9.2 Potential risks

9.2.1 For researchers and medical institution, the study may not meet the expectation and achieve the research purpose, resulting in the waste of medical resources.

9.2.2 For the patients, the fertility of the subjects may not be ultimately improved.

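### The only hypersensitivity exclusion covers the ovarian-stimulation drugs, so a woman with a known allergy to an ingredient of RECO-18 or Elevit is eligible as written (minor)

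*Combined protocol and SAP*

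**What the plan says.** Section 5.3 excludes women hypersensitive to follicle-stimulating hormone alpha, FSH, "human menopausal gonadotropin, LH or excipients". The exclusion list in the synopsis repeats the criterion in the same words. Both lists contain no other criterion on allergy or hypersensitivity.

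The randomised comparison is between two other products. Section 5.5 states that "the treatment group takes RECO-18 while the control group takes the multi-vitamins", and section 4 specifies that the control group "takes the multi-vitamins (Elevit, Bayer S.A.) with the dosage of one tablet per day". Section 2 describes RECO-18 as a functional food made from extracts of yam, clove and sophora flower bud, together with "enzymatic soybean phospholipids". Table 1 and section 8.3 add vitamins and minerals.

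On safety, section 6.3 says: "Safety indexes are adverse events occurring in the treatment group and the control group, such as gastrointestinal reactions and allergies". Section 9.2 gives one risk to participants: "For the patients, the fertility of the subjects may not be ultimately improved". It names no physical reaction to either product.

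**The concern.** The plan accepts that hypersensitivity is a reason not to enrol a woman, and it counts allergies among the events to be monitored. It applies the exclusion only to background drugs, which are not under test, and leaves out the two products that the trial itself assigns.

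What is at stake is mainly participant safety. A woman who already knows that she reacts to soy, for example, could be randomised to take it daily through one menstrual cycle and on to oocyte retrieval in the next. There is also a consequence for the trial as a whole: section 9.3.2 calls for an immediate stop to the study if serious adverse events occur. A foreseeable serious allergic reaction could therefore affect more than the one participant.

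**Working it through.** The plan states no figure on this point, so there is none to reproduce. The check is one of text, followed by a rough size.

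**Does any other provision close the gap?**

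- *The excipients wording in the criterion.* It ends the list of gonadotropins and in context means their excipients. Even read loosely, it would not reach the soy and plant ingredients of RECO-18.
- *The exclusion for contraindications (synopsis and 5.3).* It concerns assisted reproduction and pregnancy, not tolerance of a supplement.
- *The inclusion criterion on suitability for IVF/ICSI (synopsis and 5.2).* It concerns the procedure.
- *History at V1 (follow-up table).* A history is taken before treatment, but no rule ties an allergy history to eligibility.
- *Exit criteria (5.4).* They act after enrolment and do not mention allergy.

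None of the five reaches the randomised products. The woman is eligible as written.

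**How many women?**

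Inputs: 80 women, 40 per arm, 1:1 (synopsis and section 5.1). Prevalence p of a known allergy to a RECO-18 ingredient: not in the documents, assumed 0.5% to 2%. No screening by judgement is assumed.

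- Expected number exposed in the RECO-18 arm = 40 × p: 40 × 0.005 = 0.2; 40 × 0.02 = 0.8.
- Chance of at least one exposed = 1 − (1 − p)^40: 1 − 0.995^40 = 0.18; 1 − 0.98^40 = 0.55.
- Expected number among all 80 who would not be enrolled under an extended criterion = 80 × p: 80 × 0.005 = 0.4; 80 × 0.02 = 1.6.

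The first line measures exposure. The last measures the cost to recruitment. They differ by a factor of two because half of the women with such an allergy would be allocated to the control arm. The documents do not list the ingredients of Elevit, so the exposure figure is worked for RECO-18 only.

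**Effect on the analysis**

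Section 7.1 puts every randomised woman with at least one treatment in the full analysis set, and section 7.2 bases the primary analysis on that set. A woman who reacts after one dose and stops is therefore still counted. Only a woman who never takes a dose drops out, and one such woman is 1/40 = 2.5% of an arm. A woman who stops might leave the per-protocol set, but section 7.1 leaves major violations to be defined later, so this cannot be settled from the text.

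**The case against.** The strongest case on the other side is that this is a wording point of little consequence. RECO-18 is described in section 8.3 as a food for special dietary use that passed third-party inspection. History is taken at V1, consent is voluntary, and a woman who knows of her allergy can decline or be turned away by the investigator. Fewer than one exposed woman is expected even at the top of the assumed range. Most of this stands, and it is why the point is minor. It does not remove the gap, because a written criterion should not depend on an unwritten exclusion by judgement.

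A reader might infer more than the documents support, in four respects:

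- *That sections 5.3, 6.3 and 9.2 contradict each other.* They do not. One says who is excluded, one which events are monitored, one what risks are foreseen. The fault is an omission.
- *That section 6.3 attributes allergies to the randomised products.* It refers only to events in the two groups, "such as gastrointestinal reactions and allergies". Section 6.1 also counts drug reactions and reactions to ovarian stimulation as adverse events, so allergy to the stimulation drugs fits equally well.
- *That withdrawals would fall mainly in one arm and weaken the randomised comparison.* No passage reports or predicts this, and the definition of the full analysis set limits the effect.
- *That women are not warned of product reactions.* Section 5.6 requires the consent form to set out potential risks, and the consent pages are not available for review. Section 9.2 shows only that the protocol's own risk list names no such reaction.

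**Conclusion.** The point holds as a minor eligibility and safety gap. Neither exclusion list reaches allergy to RECO-18, Elevit or their ingredients, and no other provision does so. This rests on the text alone.

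The size, 0.2 to 0.8 women exposed in the RECO-18 arm, rests on the assumed prevalence of 0.5% to 2% and scales in proportion to it. Sample size, power and the significance level are unaffected, and the effect on the primary analysis is negligible. The reason to act is that the possible harm is avoidable at almost no cost, not that the result of the trial is at risk.

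**What to change.** In one amendment:

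1. Extend the existing hypersensitivity criterion, in both the synopsis and section 5.3, to known allergy to an ingredient of either randomised product.
2. State that allergy history is recorded under History at V1, so that the criterion can be applied before randomisation.
3. List in section 9.2 the gastrointestinal and allergic reactions that section 6.3 already monitors, and check that the consent form agrees.

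The cost is one eligibility line (in both places), one risk line and one recorded item at V1. On the assumed prevalence, at most one or two women would not be enrolled. No dose, schedule or analysis changes.
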